8.7.2 Effectiveness Analyses

Effectiveness analyses will be conducted on the Full Analysis Set.

Descriptive analyses of the secondary endpoints will be performed. Secondary variables will be summarized. For continuous data, the mean, standard deviation (SD), median, range (min, max) and interquartile range (Q1, Q3) will be presented. Categorical data will be displayed by absolute and relative frequencies (percentages).

Secondary time-to-event endpoints will be analyzed using Kaplan-Meier product limit methods to estimate the survival distributions and the median time-to-event. The time to endpoint will be defined as an interval between the date of enrolment (date of first visit) and date of first occurrence of the event. For patients who are event free, the censoring time will be calculated as a time interval between date of enrolment and the patient's final contact with available data concerning the event. The estimates and graphical presentation will be performed via Kaplan-Meier approach.

Further analyses will be performed to investigate the validity of results in this non-interventional study, e.g. time-dependent confounding, informative censoring, informative treatment changes/discontinuations, heterogeneity of results, and how to handle missing data. These will be described in the SAP.

Corresponding 95% confidence intervals will be provided, where appropriate.

Full details of the statistical analyses will be described in a SAP.

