6.2 STUDY BACKGROUND

OCREVUS® (ocrelizumab) was approved by the United States (US) Food and Drug Administration (FDA) on March 28, 2017, as first medication for the treatment of adult patients with relapsing forms of MS (RMS) as well as PPMS (Genentech Inc., 2017). In

clinical studies ocrelizumab has demonstrated a favorable benefit/risk profile in RMS and PPMS patients (Hauser et al. 2017; Montalban et al. 2017).

The 96-week, phase 3 OPERA I & II trials reached all relevant clinical endpoints and ocrelizumab demonstrated consistent efficacy in the overall population of RMS patients. Compared with the active comparator, interferon beta-1a, ocrelizumab was associated with a significantly lower annualized relapse rate, a significantly reduced percentage of patients with disability progression confirmed at 12 and 24 weeks (both in the pre-specified pooled analysis and in each of the two phase 3 trials separately) and with an increased percentage of patients with disability improvement confirmed at 12 weeks. These findings were supported by a significantly greater suppression of brain lesions (Hauser et al. 2017).

In patients with PPMS, the phase 3 ORATORIO study demonstrated superior efficacy of ocrelizumab versus placebo with respect to the risk of confirmed disability progression at 12 and 24 weeks, ambulation speed as assessed by the timed 25-foot walk, change in the total volume of brain lesions on T2-weighted images, and change in brain volume (Montalban et al., 2017).

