8.3.2 Secondary Outcome Measures

The secondary outcome measures for this study are as follows:

- long-term effectiveness
 - treatment success (proportion of patients with no clinical disease activity measured by relapse and disease progression and no treatment discontinuation due to adverse events [excluding pregnancies] and lack of effectiveness)
 - o proportion of patients with relapses
 - proportion of patients with confirmed disability progression (CDP)
 - o time to onset of CDP
 - o time to onset of confirmed disability improvement (CDI)
 - o Patient reported Outcomes: treatment satisfaction
- other safety endpoints:
 - o incidence of all adverse events
 - o incidence of serious infections
 - o incidence of malignancies
 - o mortality rate due to malignancies

Exploratory Outcome Measures

The exploratory outcome measures for this study are as follows:

- · change from baseline in magnetic resonance imaging (MRI) lesions
- change from baseline in global impression on the disease course as reported by physician and patient using the 'Clinical Global Impression (CGI)' scale

 change from baseline in pharmacoeconomic outcomes as measured by 'Work Productivity and Activity Impairment Questionnaire: Multiple Sclerosis (WPAI:MS)'

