8.4 DATA SOURCES

8.4.1 Collection of Data on the electronic CRF (eCRF)

Patients' data will be recorded on electronic case report forms (eCRFs). The degree of detail and completeness of data collected is dependent on local clinical practice. Data from patient notes should be entered on the eCRF as soon as they become available.

8.4.2 Data Collected during the Observation Period

During therapy with ocrelizumab, laboratory assessments are expected to be routinely performed in accordance with current guidelines and local standard of care. In the routine care setting, patients are seen regularly by their treating physicians either for treatment or for regular assessments after treatment. When performed during the observational period, available results from the range of assessments described below will be documented on the eCRF. Most data will be documented at baseline and approximately every six months according to standard of care. The proposed assessments and suggested timings for assessments in the protocol/observational plan are not mandatory. It is up to the treating physician to perform and document the assessments as performed in the real clinical setting.

All AEs occurring during the observational period will be reported. In addition, laboratory parameters (blood cell count, immunoglobulins, liver enzymes, and renal status), vital signs and weight will be recorded as available at baseline and every six months.

Effectiveness of treatment will be assessed via MS specific symptoms, relapses, and Expanded Disability Status Scale (EDSS) at baseline and approximately every six months and via MRI if available. Patient reported outcomes (PRO) regarding quality of life (QoL) and pharmacoeconomic outcomes will be collected at baseline and every six months or less frequently via questionnaires. Although the completion of such questionnaires is not routine practice it is allowed according to local regulations.

The following data will be collected during the study, as part of the local routine clinical practice:

Baseline (Study enrollment):

- Documentation of written informed consent
- Patient demographic information,
- Weight and height
- Medical history and comorbidities (including significant medical and surgical history, previous malignancies and precancerous lesions)
- Vital signs (blood pressure [BP], heart rate [HR], body temperature)

- Ocrelizumab administration information (e.g., start date, dose, dosing frequency)

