- Prior use and duration of therapies for MS and prior use and duration of immunomodulatory, immunosuppressive, and anti-neoplastic agents (if any)
- f Including significant medical and surgical history, previous malignancies and precancerous lesions
- Including tobacco use history, alcohol use history, family disease history (e.g., genetic testing such as BRCA1 and 2), personal history of malignancy, or other risk factors
- ⁿ Up to 3 months prior to enrollment
- Dates of administration (start, stop, and restart dates), dose, dosing frequency, reason for discontinuation (if applicable)
- Including MS relapse during treatment period, MS type changes, date of last administration of ocrelizumab (if applicable), MS treatment changes and rationale, most recent EDSS score since last encounter (if available), most recent MRI results since last encounter (if available)
- Including gynecological consultation, breast check, dermatological check, or other malignancy/cancer detection tests (e.g., mammography, Pap test, colonoscopy, laboratory malignancy markers)
- Blood cell count, immunoglobulins, liver enzymes, renal status, clinical chemistry, flow cytometry, viral serology
- Patient-reported, female patients
- ⁿ TSQM1.4, MSIS-29v2, CGI, SDMT. Collected every six months
- WPAI:MS. Collected every six months
- P AESIs are Hy's Law and STIAMP only
- ^q Questionnaire regarding in-depth malignancy information will be solicited from the patient's oncologist (only collected if a malignancy is identified)
- Including number of attempts to contact patient, method of contact, and reasons for early termination (e.g., death, withdrawal of consent, lost to follow-up)
- s If applicable

All assessments will be performed per standard of care (SoC). There are no mandated study visits, and data from any encounter with the neurologist during follow-up will be entered by clinicians (anticipated to occur every ~6 months). Follow-up is planned regardless of whether patients discontinue treatment with ocrelizumab. Please see Table 1 in section 8.4.2 for the data collection overview (as per standard of care with exception of questionnaires) during the treatment period.

8.4.3 Data Collected at Study Completion

All patients treated with at least one dose of ocrelizumab will be observed for the whole period of at least 7.5 and up to 10 years, regardless whether ocrelizumab treatment is discontinued during the course of the study. For patients who complete this observation

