8.7.3 Other analyses

Subgroup Analyses

- Subgroup analyses for the primary and secondary endpoints will be performed according to SAP and will comprise:
 - EDSS at baseline
 - By pre-treatment
 - Age
 - Gender (male vs. female)

Sensitivity analyses

In order to investigate the relationship between potential prognostic or risk factors and the main outcome, various exploratory analyses are imaginable. Further details will be given in the SAP.

8.7.4 Interim/Final Analysis and Timing of Analyses

Annual interim analyses are planned starting when 1-year data of at least 500 patients are available. The final analysis is planned after final database lock.

Interim analysis reports will include all analyses planned for all endpoints. In absence of hypothesis testing, α levels will not be adjusted for multiplicity.

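### Censoring CDP and CDI at the last EDSS keeps patients at risk where no event can yet be confirmed, so early interim reports understate the risk

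*Protocol*

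**What the plan says.** Section 8.3.2 of the protocol lists two time-to-event outcomes among the secondary measures: "time to onset of CDP" and the matching time to onset of CDI. Section 8.7.2 gives one Kaplan-Meier rule for all secondary time-to-event endpoints. Time runs from enrolment to the "date of first occurrence of the event". For a patient without an event, "the censoring time will be calculated as a time interval between date of enrolment and the patient's final contact with available data concerning the event". No separate rule is given for endpoints that need confirmation.

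Section 8.4.2 expects "Expanded Disability Status Scale (EDSS) at baseline and approximately every six months". It adds, below Table 1: "There are no mandated study visits, and data from any encounter with the neurologist during follow-up will be entered by clinicians". The protocol sets no confirmation interval for this study. The phrase "disability progression confirmed at 12 and 24 weeks" in section 6.2 describes the earlier phase 3 trials only.

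Annual interim analyses start when 500 patients have one-year data, which section 5 expects in Q4 2019. Under section 8.7.4, "Interim analysis reports will include all analyses planned for all endpoints".

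**The concern.** Kaplan-Meier estimation requires that a patient counted as at risk at a given time could be recorded as an event at that time. A worsening first seen at the last available EDSS has no later EDSS behind it, so it cannot be counted, yet the rule leaves the patient in the risk set there as event free. For example, a patient has EDSS at months 6 and 12 and a data cut soon after. An onset at month 6 can be confirmed at month 12. An onset at month 12 cannot be confirmed by the cut, but the patient still counts in the month-12 denominator.

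Each hazard is therefore too low, most of all where many patients have just reached their last visit: in the first interim reports and at the right-hand end of every later curve. For CDP this flatters the drug; for CDI it understates improvement. It also makes successive annual reports drift. CDP at a fixed time would rise from report to report with no change in the disease, and could be read as waning effectiveness.

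**Working it through.** The protocol gives no expected rate, count or median for CDP or CDI, so there is no stated figure to reproduce.

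**Inputs from the protocol.** 3000 patients over 30 months (section 8.1); EDSS about every 6 months (8.4.2); start in Q1 2018 and first interim in Q4 2019 (5), which is 18 to 24 months; trigger of 500 patients with one year of data (8.7.4); follow-up of 7.5 to 10 years (8.1).

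**Assumptions.** Uniform entry, so 3000/30 = 100 patients per month and the trigger is met at 5 + 12 = month 17. Onset probability *p* per six-month interval, 1% to 10%. Confirmation *g* = 6 months later (next visit) or *g* = 3 months later (an extra encounter). No loss to follow-up unless stated.

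**Formula.** Let F be follow-up at the cut. At visit *t* the rule counts everyone still event free with F ≥ *t* as at risk, but only those with F ≥ *t* + *g* can be counted as events. The estimated hazard is

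h(t) = p × P(F ≥ t+g) / P(F ≥ t),

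and the estimated risk is 1 − Π(1 − h). The true 12-month risk is 1 − (1 − p)².

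**Cut at month 21, p = 5%.** F is uniform on 0 to 21 months.

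- Next-visit confirmation. Month 6: 15 parts at risk, 9 confirmable, h = 0.05 × 9/15 = 3.0%. Month 12: 9 at risk, 3 confirmable, h = 0.05 × 3/9 = 1.67%. Risk = 1 − 0.97 × 0.9833 = 4.6%, against 1 − 0.95² = 9.75%. Shortfall 53%.
- Confirmation at 3 months. h = 0.05 × 12/15 = 4.0%, then 0.05 × 6/9 = 3.33%. Risk = 1 − 0.96 × 0.9667 = 7.2%. Shortfall 26%.

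**Other cuts, 12-month estimate** (p = 5%, true value 9.75%):

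| Cut (month) | g = 6: estimate, shortfall | g = 3: estimate, shortfall |
|---|---|---|
| 17 | 2.3%, 77% | 5.6%, 43% |
| 18 | 2.5%, 74% | 6.2%, 37% |
| 21 | 4.6%, 53% | 7.2%, 26% |
| 24 | 5.75%, 41% | 7.8%, 20% |

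The shortfall hardly depends on *p*: at month 21 and g = 6 it is 53% for p = 2% and 52% for p = 10%.

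**Drift between reports** (p = 2%, g = 6, 12-month estimate, true value 4.0%):

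- Month 21: 1 − (1 − 0.02 × 9/15)(1 − 0.02 × 3/9) = 1.9%.
- Month 33 (F from 3 to 33): 1 − (1 − 0.02 × 21/27)(1 − 0.02 × 15/21) = 3.0%.
- Month 45 (F from 15 to 45): 1 − (1 − 0.02)(1 − 0.02 × 27/30) = 3.8%.

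The same happens further along each curve. At month 33 the two-year risk is 4.8% against 7.8%.

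**Final analysis** (g = 6). Without loss, every patient has at least 90 months, so every visit up to month 84 is confirmable and the bias up to seven years is zero. With yearly loss L, each hazard is multiplied by √(1 − L): 0.975 for 5% and 0.949 for 10%. At p = 5% the seven-year risk is 1 − (1 − 0.05 × 0.975)¹⁴ = 50.3%, or 49.4% with 10% loss, against 1 − 0.95¹⁴ = 51.2%. The shortfalls are about 2% and 4%. With 10% loss the median moves from 84 to 90 months.

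**Check of the alternative.** If event-free patients are censored at the last confirmable EDSS, the denominators become those with F ≥ t+g. At month 21 and g = 6 the hazards are p × 9/9 and p × 3/3, and the 12-month risk is 9.75%, the true value.

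**The case against.** **The wording can be read another way.** For an endpoint that exists only once confirmed, the last contact with data on the event could mean the last confirmable EDSS. That reading is possible, but nothing in section 8.7.2 points to it. If both readings are open, the sentence still has to say which is meant.

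**Details belong to the SAP.** It is fair to leave the confirmation interval to the SAP, and its absence is no fault here. But the protocol does state the censoring rule. The informative-censoring work that section 8.7.2 sends to the SAP addresses a different problem: this bias arises even when censoring is wholly non-informative, as in the working above.

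**Extra encounters allow earlier confirmation.** Since any neurologist encounter is entered, some onsets may be confirmed sooner. This is why the three-month case is shown. It roughly halves the shortfall and does not remove it.

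**The consequence is limited.** The study is single-arm and descriptive, its primary objective is safety, and no decision rule uses CDP or CDI. This stands, and it limits the point to the credibility of the interim effectiveness reports.

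**Stronger readings that the protocol does not support.** A reader might infer that an onset at the last visit is always lost. At an interim cut it is only pending, and it enters the next report if confirmed. It is lost for good only at dropout or study end. A reader might also infer that the first report will be wrong by half. That is one scenario: a cut near month 21 with confirmation only at the next six-monthly visit.

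**Conclusion.** The point holds for the rule on its plain reading. The risk of CDP and CDI is underestimated and the time to event overestimated, not the reverse. At the first interim the 12-month estimate falls short by roughly 20% to 77% across cuts from month 17 to 24 and confirmation 3 to 6 months later. These figures assume uniform entry and regular six-monthly EDSS; the protocol supplies neither the hazards nor the confirmation interval.

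The final analysis is little affected: no bias up to seven years without loss, and a few percent with 5% to 10% yearly loss. It would be wrong to infer that the study's final effectiveness results are seriously distorted. The correction is worth making because the interim reports recur every year and the drift between them would be an artefact.

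**What to change.** Add to section 8.7.2, or state in the SAP with a reference from it: *For CDP and CDI, a patient without a confirmed event is censored at the last EDSS for which a later EDSS, at or beyond the confirmation interval, is available. FAS patients with no such assessment remain in the FAS, are censored at time zero, and their number is reported.* Keep the present rule for endpoints that need no confirmation. The confirmation interval must be defined for the sentence to work.

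No new data are needed. The cost is that interim curves end about one confirmation interval earlier and their confidence intervals are somewhat wider. At a month-18 cut with next-visit confirmation, no patient has a confirmable month-12 EDSS, so the 12-month estimate would not be available in that report. Early on, many patients may be censored at time zero, which is why their number should be shown.

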8.7.3 Other analyses

Subgroup Analyses

- Subgroup analyses for the primary and secondary endpoints will be performed according to SAP and will comprise:
 - EDSS at baseline
 - By pre-treatment
 - Age
 - Gender (male vs. female)

Sensitivity analyses

In order to investigate the relationship between potential prognostic or risk factors and the main outcome, various exploratory analyses are imaginable. Further details will be given in the SAP.

8.7.4 Interim/Final Analysis and Timing of Analyses

Annual interim analyses are planned starting when 1-year data of at least 500 patients are available. The final analysis is planned after final database lock.

Interim analysis reports will include all analyses planned for all endpoints. In absence of hypothesis testing, α levels will not be adjusted for multiplicity.

8.8 QUALITY CONTROL

8.8.1 Study Documentation

The physician must maintain adequate and accurate records to enable the conduct of the study to be fully documented, including but not limited to the protocol, protocol amendments, Informed Consent Forms, and documentation of EC and governmental approval/notification. In addition, at the end of the study, the physician will receive the patient data, which include an audit trail containing a complete record of all changes to data.

Roche shall ensure that the dataset and statistical programs used for generating the data included in the final study report are kept in electronic format and are available for auditing and inspection.

8.8.2 Site Audits and Inspections

Site visits will be conducted by Roche or an authorized representative for audit of study data, patients' medical records, and eCRFs.

The physician will also permit national and local health authorities to inspect facilities and records relevant to this study.

8.8.3 Retention of Records

Records and documents pertaining to the conduct of this study, including eCRFs and Informed Consent Forms, must be retained by the physician for at least 15 years after completion or discontinuation of the study, or for the length of time required by relevant national or local health authorities, whichever is longer. After that period of time, the documents may be destroyed, subject to local regulations.

No records may be disposed of without the written approval of Roche. Written notification should be provided to Roche prior to transferring any records to another party or moving them to another location.

All supporting functional parties will comply with Roche procedures regarding archiving and record management.

8.8.4 Administrative Structure

Lead Scientific Responsible of this non-interventional study is [name]. [name], University Clinic Dresden.

The study is conducted by the CRO AMS Advanced Medical Services GmbH.

8.9 LIMITATIONS OF THE RESEARCH METHOD

This study aims to evaluate the safety profile of ocrelizumab in patients with MS in a real-world setting.

Potential limitations of the study design and measures proposed to address them include the following:

Enrollment bias: Sites will be expected to maintain screening logs of all patients meeting eligibility criteria, along with reasons for non-enrollment.

Channeling bias: Factors associated with treatment choice and also with any of the study outcomes of interest will be measured at baseline (study enrollment), and will be accounted for in multivariate analyses using standard regression-based covariate adjustments or appropriate causal inference methods, as described further in Section 8.7..

Residual confounding between the study population and comparators: Data analysis will examine the univariate distributions of key variables that could cause confounding (e.g., gender, age, comorbidities), and will be accounted for in multivariate analyses.

Healthy user bias/depletion of susceptibles: Long-term users of a given medication may be at lower risk of malignancies than new users (i.e. they would have survived to the time of study enrollment). Since patients will be enrolled at the time of ocrelizumab treatment initiation, this should eliminate bias associated with the study of prevalent medication users.

Misclassification: All centers/sites will undergo standardized training and utilize standardized documentation for completing of eCRFs at enrollment and for each follow-up assessment; specifically, on the importance of accurately collecting exposure information as well as outcome variable information. However, the same rigor may not apply to the data collection in the external control cohorts.

Recruitment of patients dependent on several factors: Uptake of new medications such as ocrelizumab is unpredictable and has the potential to impact the feasibility of meeting the recruitment targets in Germany. However, continuous monitoring of patient recruitment at the site and country levels will allow strategies to be employed in response to any such challenges and to reduce or eliminate the potential impact of these

factors. These include potentially initiation of additional sites within participating countries, and/or expansion of the study into additional countries.

8.10 OTHER ASPECTS

None

